### 6.2.2. Analysis Methods for Secondary Efficacy Endpoints

For analyses of HCV RNA  $<$  LLOQ by visit while on treatment and during the posttreatment (SVR) follow-up period, subjects will be assigned a value at each visit based on the analysis visit windows specified in Section 3.8.2. Missing values will be imputed based on the categorical imputation rules described in Section 3.6.1. The 2-sided 95% exact CI based on the Clopper-Pearson method will be provided for the proportion of subjects with HCV RNA  $<$  LLOQ at each visit for each treatment group. The overall category for “HCV RNA  $<$  LLOQ” will be divided into the following 2 subcategories: “ $<$  LLOQ TND” for subjects with target not detected and “ $<$  LLOQ detected” for subjects with  $<$  LLOQ HCV RNA detected in tabular displays.

A plot of the proportion of subjects with HCV RNA  $<$  LLOQ over time during treatment will be provided.

Summary statistics will be presented for absolute values and change from baseline in HCV RNA ( $\log_{10}$  IU/mL) by visit through the EOT. Imputation rules described in Section 3.6.1 will be used to assign HCV RNA values for missing values at visits that are bracketed by “ $<$  LLOQ TND” and/or “ $<$  LLOQ detected.” Otherwise, a missing = excluded analysis will be performed. Plots of the mean  $\pm$  SD and median (Q1, Q3) absolute values and changes from baseline in HCV RNA through EOT will be provided.

For the virologic outcome analysis, a summary table of the number and proportion of subjects with SVR12, virologic failure, and other (ie, subjects who did not achieve SVR12 and did not meet criteria for virologic failure) will be created. All subjects who achieve SVR12 will be categorized as SVR12. Virologic failure will be descriptively summarized as “on-treatment virologic failure” and relapse (which will be broken down by study drug completed yes/no). The denominator for relapse will be the number of subjects who had HCV RNA  $<$  LLOQ on their last observed on-treatment HCV RNA measurement; otherwise, the denominator will be the number of subjects in the FAS. Virologic outcomes will also be provided by randomization stratum by treatment group and overall for the FAS.

In addition, a summary table of the number and proportion of subjects with HCV RNA < LLOQ and  $\geq$  LLOQ at each posttreatment follow-up visit (observed and imputed, with reasons for imputed) will be provided. Two-sided 95% exact CIs based on the Clopper-Pearson method will be presented for the proportion of subjects with HCV RNA < LLOQ by treatment group.

By-subject data listings will be provided for the HCV RNA change from baseline for subjects with virologic failure and subjects with other virologic outcomes.

Drug-resistant substitutions will be summarized and listed as applicable.

### **6.3. Exploratory Efficacy Endpoints**

#### **6.3.1. Definition of Exploratory Efficacy Endpoints**

PPD

[Redacted text]

#### **6.3.2. Analysis Methods for Exploratory Efficacy Endpoints**

PPD

[Redacted text]

### **6.4. Changes From Protocol-Specified Efficacy Analyses**

There are no planned changes from protocol-specified efficacy analyses.

## **7. SAFETY ANALYSES**

### **7.1. Adverse Events and Deaths**

#### **7.1.1. Adverse Event Dictionary**

Clinical and laboratory AEs will be coded using the current version of the Medical Dictionary for Regulatory Activities (MedDRA). System organ class (SOC), high level group term, high level term, preferred term (PT), and lower level term will be provided in the AE dataset.

#### **7.1.2. Adverse Event Severity**

Adverse events were graded by the investigator as Grade 1 (mild), 2 (moderate), 3 (severe), or 4 (life threatening) according to toxicity criteria specified in the GSI Grading Scale for Severity of Adverse Events and Laboratory Abnormalities (01 April 2015). The severity grade of events for which the investigator did not record severity will be categorized as “missing” for tabular summaries and data listings and will be considered the least severe for the purposes of sorting for data presentation.

#### **7.1.3. Relationship of Adverse Events to Study Drug**

Related AEs are those for which the investigator selected “Related” on the AE eCRF to the question of “Related to Study Treatment.” Events for which the investigator did not record the relationship to study drug will be considered to be related to study drug for summary purposes. However, by-subject data listings will show the relationship as missing from that captured on the eCRF.

#### **7.1.4. Serious Adverse Events**

Serious adverse events (SAEs) will be identified and captured as SAEs if AEs met the definitions of SAE specified in the study protocol. Serious adverse events captured and stored in the clinical database will be reconciled with the SAE database from the Gilead Drug Safety and Public Health Department before database finalization.

#### **7.1.5. Treatment-Emergent Adverse Events**

##### **7.1.5.1. Definition of Treatment-Emergent**

Treatment-emergent adverse events (TEAEs) are defined as 1 or both of the following:

- Any AEs with an onset date on or after the study drug start date and no later than 30 days after permanent discontinuation of study drug
- Any AEs leading to premature discontinuation of study drug.

#### 7.1.5.2. Incomplete Dates

If the onset date of an AE is incomplete, then the month and year (or year alone if month is not recorded) of onset determine whether an AE is treatment emergent, as long as the AE stop date is not prior to the first dose date of study drug. The event is considered treatment emergent if both of the following 2 criteria are met:

- The AE onset and end dates are the same as or after the month and year (or year only) of the first dose date of study drug
- The AE onset date is the same as or before the month and year (or year only) of the 30th day after the date of the last dose of study drug

An AE with completely missing onset and stop dates, or with the onset date missing and a stop date later than the first dose date of study drug, will be considered treatment emergent.

#### 7.1.6. Summaries of Adverse Events and Deaths

A brief high-level summary of TEAEs will show, by treatment group, the number and proportion of subjects who had the following: (1) any AE, (2) any AE of Grade 3 or above, (3) any AE of Grade 2 or above, (4) any treatment-related AE, (5) any treatment-related AE of Grade 3 or above, (6) any treatment-related AE of Grade 2 or above, (7) any SAE, (8) any treatment-related SAE, (9) any AE that led to premature discontinuation of any study drug, (10) any AE that led to modification or interruption of any study drug, (11) any AE that led to premature discontinuation of SOF/VEL, (12) any AE that led to interruption of SOF/VEL, (13) any AE that led to discontinuation of RBV, (14) any AE that led to modification or interruption of RBV, and (15) all deaths.

Summaries (number and percentage of subjects) of TEAEs (by SOC and PT) will be provided by treatment group using the safety analysis set as follows:

- All AEs
- AEs of Grade 3 or above
- AEs of Grade 2 or above
- All treatment-related AEs
- Treatment-related AEs of Grade 3 or above
- Treatment-related AEs of Grade 2 or above
- All SAEs
- All treatment-related SAEs

- AEs leading to premature discontinuation of any study drug
- AEs leading to modification or interruption of any study drug

Multiple events will be counted once only per subject in each summary. The SOC's will be presented alphabetically and the PT's within each SOC will be presented by descending order of the total frequencies. In summaries by severity grade, the most severe grade will be used for those AEs that occurred more than once in an individual subject during the study.

In addition to the above summary tables, TEAEs will also be summarized by PT only, in order of descending incidence within the overall treatment group for:

- All AEs
- AEs that occurred in at least 5% of subjects within any treatment group
- AEs of Grade 3 or above
- All treatment-related AEs
- All SAEs
- AEs leading to premature discontinuation of any study drug
- AEs leading to modification or interruption of any study drug
- AEs leading to premature discontinuation of SOF/VEL
- AEs leading to interruption of SOF/VEL
- AEs leading to modification or interruption of RBV
- AEs leading to discontinuation of RBV

Data listings, with a variable indicating whether the event is treatment emergent, will be provided for the following:

- All AEs
- AEs of Grade 3 or above
- SAEs
- Deaths
- AEs leading to premature discontinuation of any study drug

## 7.2. Laboratory Evaluations

Laboratory data collected during the study will be analyzed and summarized using both quantitative and qualitative methods. Summaries of laboratory data will be provided for the Safety Analysis Set and will include data collected up to the date of the last dose of study drug plus 30 days. The analysis will be based on values reported in conventional units. When values are below the limit of quantitation, the closest imputed value will be used for the purpose of calculating summary statistics, but the original values will be presented in listings. For example, if “< 0.2” was recorded, a value of 0.1 will be used for the purpose of calculating summary statistics; if “< 0.1” was recorded, a value of 0.09 will be used for the purpose of calculating summary statistics.

A by-subject listing for laboratory test results will be provided by subject ID number and visit in chronological order for hematology, serum chemistry, and urinalysis separately. Values falling outside of the relevant reference range and/or having a severity grade of 1 or higher, based on the GSI Grading Scale for Severity of Adverse Events and Laboratory Abnormalities, will be flagged in the data listings, as appropriate.

No inferential statistics will be generated.

### 7.2.1. Summaries of Numeric Laboratory Results

Descriptive statistics (n, mean, SD, median, Q1, Q3, minimum, and maximum) will be provided by treatment group for ALT, aspartate aminotransferase (AST), total bilirubin, alkaline phosphatase, white blood cells (WBC) counts, neutrophils, lymphocytes, hemoglobin, platelets, CD4 T-cell counts (absolute and percentage for HIV coinfecting subjects only), reticulocytes, and international normalized ratio (INR) as follows:

- Baseline values
- Values at each postbaseline visit
- Change from baseline at each postbaseline visit

A baseline laboratory value will be defined as the final assessment performed on or prior to the date/time of first dose of study drug. Change from baseline to a postbaseline visit will be defined as the visit value minus the baseline value. The mean, median, Q1, Q3, minimum, and maximum values will be displayed to the reported number of digits and the SD to the reported number of digits plus 1.

Median (Q1, Q3) of the observed values for ALT, AST, total bilirubin, alkaline phosphatase, WBC, neutrophils, lymphocytes, hemoglobin, platelets, CD4 T-cell counts (absolute and percentage for HIV coinfecting subjects only), and reticulocytes will be plotted using a line plot by treatment group and visit. In the case of multiple values in an analysis window, data will be selected for analysis as described in Section 3.8.3.

A by-subject listing of subjects with any hemoglobin values  $< 10$  g/dL and  $< 8.5$  g/dL will be provided. All laboratory test data will be listed. Central Laboratory (Covance) Reference Ranges will also be listed.

### **7.2.2. Graded Laboratory Values**

The GSI Scale for Severity of Adverse Events and Laboratory Abnormalities (01 April 2015) will be used for assigning toxicity grades (0 to 4) to laboratory results for analysis. Grade 0 includes all values that do not meet the criteria for an abnormality of at least Grade 1. Some laboratory tests have criteria for both increased and decreased levels; analyses for each direction (ie, increased, decreased) will be presented separately.

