Appendix 3. GSI Grading Scale for Severity of Adverse Events and Laboratory Abnormalities

Antiviral Toxicity Grading Scale Version: 01 April 2015

HEMATOLOGY				
	Grade 1	Grade 2	Grade 3	Grade 4
Hemoglobin HIV POSITIVE Adult and Pediatric ≥ 57 Days	8.5 to 10.0 g/dL 85 to 100 g/L	7.5 to < 8.5 g/dL 75 to < 85 g/L	6.5 to < 7.5 g/dL 65 to < 75 g/L	< 6.5 g/dL < 65 g/L
HIV NEGATIVE Adult and Pediatric ≥ 57 Days	10.0 to 10.9 g/dL 100 to 109 g/L OR Any decrease from Baseline 2.5 to < 3.5 g/dL 25 to < 35 g/L	9.0 to < 10.0 g/dL 90 to < 100 g/L OR Any decrease from Baseline 3.5 to < 4.5 g/dL 35 to < 45 g/L	7.0 to < 9.0 g/dL 70 to < 90 g/L OR Any decrease from Baseline ≥ 4.5 g/dL ≥ 45 g/L	< 7.0 g/dL < 70 g/L
Infant, 36–56 Days (HIV POSITIVE OR NEGATIVE)	8.5 to 9.4 g/dL 85 to 94 g/L	7.0 to < 8.5 g/dL 70 to < 85 g/L	6.0 to < 7.0 g/dL 60 to < 70 g/L	< 6.0 g/dL < 60 g/L
Infant, 22–35 Days (HIV POSITIVE OR NEGATIVE)	9.5 to 10.5 g/dL 95 to 105 g/L	8.0 to < 9.5 g/dL 80 to < 95 g/L	7.0 to < 8.0 g/dL 70 to < 80 g/L	< 7.0 g/dL < 70 g/L
Infant, 1–21 Days (HIV POSITIVE OR NEGATIVE)	12.0 to 13.0 g/dL 120 to 130 g/L	10.0 to < 12.0 g/dL 100 to < 120 g/L	9.0 to < 10.0 g/dL 90 to < 100 g/L	< 9.0 g/dL < 90 g/L
Absolute Neutrophil Count (ANC) Adult and Pediatric, ≥ 7 Months#	1000 to 1300/mm ³ 1.00 to 1.30 GI/L	750 to < 1000/mm ³ 0.75 to < 1.00 GI/L	500 to < 750/mm ³ 0.50 to < 0.75 GI/L	< 500/mm ³ < 0.50 GI/L
Absolute CD4+ Count HIV NEGATIVE ONLY Adult and Pediatric > 13 Years	300 to 400/mm ³ 300 to 400/μL	200 to < 300/mm ³ 200 to < 300/μL	100 to < 200/mm ³ 100 to < 200/μL	< 100/mm ³ < 100/μL

HEMATOLOGY				
	Grade 1	Grade 2	Grade 3	Grade 4
Absolute Lymphocyte Count HIV NEGATIVE ONLY Adult and Pediatric > 13 Years	600 to 650/mm ³ 0.60 to 0.65 GI/L	500 to < 600/mm ³ 0.50 to < 0.60 GI/L	350 to < 500/mm ³ 0.35 to < 0.50 GI/L	< 350/mm ³ < 0.35 GI/L
Platelets	100,000 to < 125,000/mm ³ 100 to < 125 GI/L	50,000 to < 100,000/mm ³ 50 to < 100 GI/L	25,000 to < 50,000/mm ³ 25 to < 50 GI/L	< 25,000/mm ³ < 25 GI/L
WBCs	2000/mm ³ to 2500/mm ³ 2.00 GI/L to 2.50 GI/L	1,500 to < 2,000/mm ³ 1.50 to < 2.00 GI/L	1000 to < 1,500/mm ³ 1.00 to < 1.50 GI/L	< 1000/mm ³ < 1.00 GI/L
Hypofibrinogenemia	100 to 200 mg/dL 1.00 to 2.00 g/L	75 to < 100 mg/dL 0.75 to < 1.00 g/L	50 to < 75 mg/dL 0.50 to < 0.75 g/L	< 50 mg/dL < 0.50 g/L
Hyperfibrinogenemia	> ULN to 600 mg/dL > ULN to 6.0 g/L	> 600 mg/dL > 6.0 g/L	— —	— —

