#### **7.2.2.2. Summaries of Treatment-Emergent Laboratory Abnormalities**

The following summaries (number and percentage of subjects) for treatment-emergent laboratory abnormalities will be provided by analyte and treatment group; subjects will be categorized according to the most severe postbaseline abnormality grade for a given analyte:

- Graded laboratory abnormalities
- Grade 3 or above laboratory abnormalities

For all summaries of laboratory abnormalities, the denominator is the number of subjects with nonmissing postbaseline values up to 30 days after the date of the last dose of study drug for the laboratory parameter of interest.

A by-subject listing of treatment-emergent Grade 3 or above laboratory abnormalities will be provided by subject ID number and visit in chronological order. This listing will include all test results that were collected throughout the study for the analyte of interest, with all applicable severity grades or abnormal flags displayed.

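### The graded laboratory tables pool haemoglobin grades from two different HIV-specific scales and keep HIV-positive subjects, whose lymphocytes the scale does not grade, in the lymphocyte denominator

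*SAP*

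**What the plan says.** HIV-coinfected subjects are eligible on additional criteria (Protocol 4.2), with no stated cap. Randomization is stratified by prior treatment experience only (Protocol 3.1, SAP 3.3).

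Protocol 9.6.3 requires the Appendix 3 scheme for graded laboratory abnormalities. SAP 7.2.2 follows it: the scale "will be used for assigning toxicity grades (0 to 4) to laboratory results for analysis". It adds a default: "Grade 0 includes all values that do not meet the criteria for an abnormality of at least Grade 1".

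In Appendix 3 the adult haemoglobin row depends on HIV status. One row is headed "Hemoglobin HIV POSITIVE Adult and Pediatric ≥ 57 Days" and has no criterion based on a fall from baseline. The HIV-negative row has such criteria; its Grade 3 cell reads "7.0 to < 9.0 g/dL 70 to < 90 g/L OR Any decrease from Baseline ≥ 4.5 g/dL ≥ 45 g/L". The only lymphocyte row is headed "Absolute Lymphocyte Count HIV NEGATIVE ONLY Adult and Pediatric > 13 Years".

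SAP 7.2.2.2 says that the summaries "will be provided by analyte and treatment group; subjects will be categorized according to the most severe postbaseline abnormality grade". For all of them, "the denominator is the number of subjects with nonmissing postbaseline values up to 30 days after the date of the last dose" of study drug. Neither section mentions HIV status.

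**The concern.** Two things go wrong when these rules meet a mixed population.

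- **Lymphocytes.** A coinfected subject's value can meet no grading criterion, so it defaults to Grade 0. The subject has a nonmissing value and stays in the denominator. Someone who could not be counted as an event is counted as a non-event.
- **Haemoglobin.** A Grade 3 in the pooled table means one thing for HIV-negative subjects and another for HIV-positive subjects. The pooled percentage therefore depends on the HIV mix of the arm as well as on the haemoglobin values.

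Safety and tolerability of each regimen is a primary objective, and the arms differ by ribavirin. In its account of ASTRAL-3 (Protocol 1.2.2.1.3), the protocol attributes the excess of Grade 3 laboratory abnormalities with SOF+RBV mainly to haemoglobin. A reader comparing the arms would naturally turn to the Grade 3 or above table.

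**Working it through.** The plan gives no figure on this point. Its only design figure, an exact 95% interval at most 21% long with 100 subjects per arm, reproduces (the longest Clopper-Pearson interval is 20.3%, at 50 of 100) and plays no part below.

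**1. The two haemoglobin rows (Appendix 3, adults, g/dL)**

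| Grade | HIV-positive | HIV-negative |
|---|---|---|
| 1 | 8.5 to 10.0 | 10.0 to 10.9, or fall 2.5 to <3.5 |
| 2 | 7.5 to <8.5 | 9.0 to <10.0, or fall 3.5 to <4.5 |
| 3 | 6.5 to <7.5 | 7.0 to <9.0, or fall ≥4.5 |
| 4 | <6.5 | <7.0 |

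The same result on each row:

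| Result | HIV-positive | HIV-negative |
|---|---|---|
| 8.6 from 13.0 | 1 | 3 |
| 8.0 from 13.0 | 2 | 3 |
| 6.8 from 13.0 | 3 | 4 |
| 10.4 from 15.0 (fall 4.6) | 0 | 3 |

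On a 0.1 g/dL grid (baseline 10.0 to 16.9, later value 5.0 to 16.9), no result gets a higher grade on the HIV-positive row. Applying the SAP's treatment-emergent rule on that grid, no result is Grade 3 or above on the HIV-positive row without also being so on the HIV-negative row. The grid starts at 10.0 because screening haemoglobin below 10 g/dL is exclusionary.

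**2. Lymphocyte dilution**

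Let p be the rate among subjects who can be graded and h the coinfected share of the denominator. Then reported rate = p × (1 − h). Neither p nor h is in the documents. With p = 10% assumed:

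- h = 0: 10%
- h = 10%: 9%
- h = 20%: 8%
- h = 30%: 7%
- h = 40%: 6%

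In counts, with 100 in an arm and 30 coinfected, 7 events among 70 gradable subjects is 10%, but the table shows 7/100 = 7%.

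**3. Haemoglobin, upper bound**

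Take the HIV-negative row as the yardstick. Assume Grade 3 or above rates of 10% with ribavirin and 1% without, the same underlying rate in coinfected and other subjects, and an equal HIV share in both arms. If no coinfected subject reaches Grade 3 on their own row, the difference between arms is (10 − 1) × (1 − h) points: 8.1, 7.2 or 6.3 at h = 10%, 20% or 30%, against 9.0. The real loss would be smaller, because a coinfected subject below 7.5 g/dL is still Grade 3 or above.

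**4. Chance imbalance between arms**

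With h = 30% and 100 per arm, the SD of the difference in coinfected share is √(2 × 0.3 × 0.7/100) = 6.5 points. At p = 10% this moves the difference in rates by 0.10 × 6.5 = 0.65 points. The standard error of a single 10% rate is √(0.1 × 0.9/100) = 3.0 points, so imbalance is a side issue.

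**The case against.** The strongest reply is that the SAP does what Protocol 9.6.3 requires, and that little of the haemoglobin evidence rests on grades. This largely stands. The SAP also plans:

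- a table and a listing of subjects below 10 and below 8.5 g/dL, on one scale for everyone (15.11.6.1.5.2, 16.2.8.1.1);
- haemoglobin and lymphocytes with change from baseline by visit, for all subjects (15.11.6.1.5.1, 15.11.6.1.9);
- adverse events leading to modification, interruption or discontinuation of ribavirin (SAP 7.1.6).

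The primary safety endpoint is an adverse event leading to permanent discontinuation of study drug (Protocol 9.1.2), and it uses no laboratory grade.

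Three stronger readings are tempting, and the documents do not support them.

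- **That ribavirin's main toxicity is understated overall.** The outputs above do not use the HIV-specific rows. Understated also presumes that the HIV-negative row is the correct one for everyone, which the documents do not say. Nor can lymphocytes carry that claim. The protocol names them among the commonest Grade 3 or 4 haematology findings in ASTRAL-4, a decompensated population, and attributes those findings to ribavirin or to the liver disease.
- **That the grades contradict Protocol Table 7-1.** That table gives dose-modification values, and Appendix 3 gives severity grades. Nothing requires them to agree, and they do not for HIV-negative subjects either: 8.6 g/dL is Grade 3 but above the table's 8.5, and 9.5 g/dL can be Grade 2 but is below its 10.
- **That everyone should be graded on the HIV-negative row.** Doing so in place of the protocol scale would depart from Protocol 9.6.3 and make SAP 7.8, which reports no deviations, untrue.

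What the reply does not answer is the arithmetic of the graded tables. Following Appendix 3 does not require subjects it cannot grade to be counted as Grade 0, or two unlike rows to be added together. The other outputs do not replace these tables: the threshold table misses large falls that end above 10 g/dL, and by-visit summaries do not count subjects with severe abnormalities.

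**Conclusion.** The point holds for the graded laboratory tables (15.11.6.3.1 and 15.11.6.3.2) and the matching Grade 3 or above listing (16.2.8.1.3), and no further. In the tables, the graded lymphocyte rate is too low by a relative amount equal to the coinfected share of the denominator. The pooled haemoglobin grades mix two scales and vary with the HIV mix. In the listing, a coinfected subject can be absent with a value that would list an HIV-negative subject.

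The size rests on two assumptions: the coinfected share (10% to 40%) and the underlying rate (10%). On those, the lymphocyte rate shows as 9% to 6%. If no coinfected subject enrols, the effect is zero. Severity: minor.

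**What to change.** In SAP 7.2.2.2:

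- restrict the denominator for graded lymphocyte abnormalities to HIV-negative subjects;
- present graded haemoglobin by HIV status within each arm, using the Appendix 3 row that applies to each subject;
- footnote both tables to say which row and denominator were used, and how a subject with missing HIV status (a category allowed in SAP 3.4 and 5.2) is handled.

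Keep the planned table of haemoglobin below 10 and below 8.5 g/dL as the common-scale summary.

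No new data are needed. HIV status is already a baseline characteristic and a planned subgroup, and the change stays within Protocol 9.6.3. The cost is some SAP wording and a few extra table rows, in which the coinfected subgroups may be small.

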#### **7.2.2.1. Treatment-Emergent Laboratory Abnormalities**

Treatment-emergent laboratory abnormalities are defined as values that increase at least 1 toxicity grade from baseline at any postbaseline time point, up to the date of the last dose of study drug plus 30 days. If the relevant baseline laboratory value is missing, then any abnormality of at least Grade 1 at a postbaseline time point will be considered treatment emergent.

